4.4.1.2.5 Duration

Duration is derived from the start and end dates of the unsolicited AE:

$$\text{Duration} = \text{stop date of unsolicited AE} - \text{start date of unsolicited AE} + 1$$

The duration should be considered as missing only if one or both of the start and end dates of the unsolicited AE is missing or partially missing.

For those participants receiving a non-study authorized/approved COVID-19 vaccine (eg, on Day X), the duration is categorized as following:

- If an unsolicited AE with both time of onset and stop date before Day X, then the duration for that AE will be derived same as above.
- If an unsolicited AE with time of onset before Day X and the corresponding stop date is on or after Day X, then the duration will be derived as Missing.

Duration will be displayed by period as following:

- 1-3 days
- 4-7 days
- 8 days or more
- Missing

4.4.1.3 SAEs

SAEs will be analyzed throughout the study using the following periods:

- Within 21 days after each injection
- During the study (ie, all SAEs occurred during the entire study or the cutoff date which corresponds to the date of any interim analysis)

Note: SAE that occurred before vaccination (negative time of onset) will not be included in analysis but will be listed separately.

Main safety analysis will include only those SAEs with time of onset before a participant received a non-study authorized/approved COVID-19 vaccine, if applicable. SAEs with time of onset on or after the date of receiving a non-study authorized/approved COVID-19 vaccine will be listed separately.

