**Table 3.1: Objectives and endpoints**

Objectives	Endpoints
Primary	

Safety
 
To describe the safety profile of all participants in each age group and each study intervention group up to 12 months post-last dose.
	
Safety
 
 
• Presence of unsolicited systemic AEs reported in the 30 minutes after each injection
 
• Presence of solicited injection site reactions and systemic reactions (pre-listed in the participant's Diary Card [DC] and Case Report Form [CRF]) occurring up to 7 days after each injection
 
• Presence of unsolicited AEs reported up to 21 days after each injection
 
• Presence of medically attended adverse events (MAAEs) throughout the study
 
• Presence of serious adverse events (SAEs) and adverse events of special interest (AESIs) throughout the study
 
• Presence of out-of-range biological test results up to 8 days post-last dose (ie, up to Day [D] 09 for Cohort 1 and up to D30 for Sentinel Cohort and Cohort 2)
 

Objectives	Endpoints

Immunogenicity
 
To describe the neutralizing antibody profile at D01, D22, and D36 of each study intervention group.
	
Immunogenicity
 
Neutralizing antibody titers against the SARS-CoV-2 D614G variant will be measured with the neutralization assay
 
 
• Antibody titer at D01, D22, and D36
 
• Fold-rise (fold-rise in serum antibody neutralization titer post-vaccination relative to D01) at D22, and D36
 
• 2-fold and 4-fold-rise in serum neutralization titer (post/pre) relative to D01 at D22, and D36
 
• Occurrence of neutralizing antibody seroconversion defined as baseline values below lower limit of quantification (LLOQ) with detectable neutralization titer above assay LLOQ at D22 and D36
 

Secondary	

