#### Authorized for emergency use and Approved SARS-CoV-2 vaccines

If an approved/authorized SARS-CoV-2 vaccine is available in the country or region where the study is conducted, investigators will discuss this information with prospective study participants at the time of informed consent who will be encouraged to obtain the approved/authorized SARS-CoV-2 vaccine if applicable to them. Recruitment and enrollment of eligible participants will proceed only if, despite encouragement, the candidate participant expresses no intention to seek an authorized or approved vaccine at least until completion of the key follow-up timepoint (D43) of this study for informing progression to further clinical development and dose selection.

If the participant is enrolled and seeks vaccination of an authorized/approved COVID-19 vaccine outside of the study, he/she will be encouraged to discuss this intention proactively with the study investigator and will be permitted to receive the authorized vaccine at any time. If the participant receives the authorized/approved COVID-19 vaccine, this information would be collected and the participant's data up to the point of receipt of authorized/approved COVID-19 vaccine will be included in the primary analysis for immunogenicity and safety. Participants will continue to be followed for the duration of the study as per scheduled visits and procedures. Participants will be invited to a visit prior to receiving the vaccine and requested to provide a blood sample for immunological assessment. Participants will not receive the second vaccination if they have received the authorized/approved COVID-19 vaccine between the first and second scheduled vaccination.

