After the planned preliminary interim of the Sentinel Cohort participants, a decision to discontinue the development of the mRNA COVID-19 vaccine was made. On September 27, 2021, all Investigators were informed to terminate further vaccinations and enrollment. All enrolled participants were to be unblinded to allow them to make their decision to receive an authorized COVID-19 vaccine. All clinical sites were to contact participants to inform them of the discontinuation of further study vaccinations, told what intervention they received and invited to come in for an unscheduled visit for counseling to answer any questions about the study, to discuss available options for receipt of an approved /authorized COVID vaccination, and were requested to provide unscheduled blood draw for serological assessment (UBXX). Participants were informed that additional D22 or D36 blood draws for serological assessment would be appreciated but are not mandatory. No protocol defined schedule visits or blood draws at timepoints later than D36 were required. Monitoring for SAEs, AESIs, medically attended AEs, and pregnancy and collection of influenza and COVID-19 vaccines were continued with safety calls. On March 15, 2022, after concurrence from regulatory authorities, Investigators were notified of the decision to end the study at the 6-month safety follow-up instead of 12-month follow-up.

This version 5.0 of SAP is updated for the final unblinded analysis. The sections of Trial Objectives and Trial Design and Plan are kept the same with the final protocol, but modifications are made in Section 4 and Section 5 for endpoint derivation, statistical methods, and populations used in analyses, to reflect the changes needed for the final analyses.

2 Trial Objectives

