2.1 Primary Objectives

Safety

To describe the safety profile of all participants in each age group and each study intervention group up to 12 months post-last dose.

Immunogenicity

To describe the neutralizing antibody profile at D01, D22, and D36 of each study intervention group.

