4.4.1.5.7 AESI

AESIs will be collected throughout the study to ensure that events are communicated to the Sponsor in an expedited manner and followed-up until the end of the follow-up period or resolution, as per the assigned causality.

AESIs will include:

- Protocol-specified AESIs: Anaphylactic reactions, generalized convulsions, Guillain-Barré Syndrome (GBS), acute disseminated encephalomyelitis (ADEM), thrombocytopenia, and vasculitides
- New-onset chronic medical conditions (NOCMCs)
- AESIs related to SARS-CoV-2 infection and COVID-19 disease (see Appendix 10.5 of the protocol).

NOCMCs are defined as any new ICD-10 diagnosis (10th revision of the International Statistical Classification of Diseases and Related Health Problems) that is applied to the participant during the course of the study, after receipt of the study agent, that is expected to continue for at least 3 months and requires continued health care intervention.

AESIs will be analyzed throughout the study using the following periods:

- Within 21 days after each injection
- During the study (ie, all AESIs occurred during entire the study or the cutoff date which corresponds to the date of any interim analysis)

Note: AESI with time of onset before first vaccination (negative time of onset) will not be included in analysis but will be listed separately.

Main safety analysis will include only those AESIs with time of onset before a participant received a non-study authorized/approved COVID-19 vaccine, if applicable. AESIs with time of onset on or after the date of receiving a non-study authorized/approved COVID-19 vaccine will be listed separately.

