4.4.1.5.8 MAAE

A MAAE is a new onset or a worsening of a condition that prompts the participant to seek unplanned medical advice at a physician’s office or Emergency Department. Physician contact made over the phone or by e-mail will be considered a physician office visit for the purpose of MAAE collection. This includes medical advice seeking during the study visit or routine medical care. This definition excludes pediatric check-ups, follow-up visits of chronic conditions with an onset prior to entry in the study and solicited reactions.

MAAEs will be analyzed during the following time periods:

- Within 21 days after each injection
- During the study (ie, all MAAEs occurred during entire the study or the cutoff date which corresponds to the date of any interim analysis)

Note: MAAEs with date of onset before first vaccination (negative time of onset) will not be included in analysis but will be listed separately.

Main safety analysis will include only those MAAEs with time of onset before a participant received a non-study authorized/approved COVID-19 vaccine, if applicable. MAAEs with time of onset on or after the date of receiving a non-study authorized/approved COVID-19 vaccine will be listed separately.

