In addition, the following analyses planned at the time of the protocol or previous version of SAPs will not be performed:

- Between groups ratios of neutralizing Ab GMTs and between group seroconversion rates differences
- Between groups ratios of anti-S antibody concentrations and between group seroconversion rates differences
- Correlated of risk and of vaccine efficacy
- Complementary analysis and sensitive analysis on immunogenicity data and safety data
- Safety and immunogenicity analyses by aggregated groups

Detailed analyses can be found in the SAP document of Tables, Listings and Figures.

6 References List

4. Newcombe RG. Two-sided confidence intervals for the single proportion: comparison of seven methods. *Stat Med.* 1998;17(8):857-72.
5. Agresti, Alan (2002). *Categorical Data Analysis (Second ed.)*. Wiley. ISBN 0-471-36093-7.

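### SAEs, AESIs and MAAEs that start after an outside COVID-19 vaccine are only listed, so the planned by-group safety summaries stop at that vaccine

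*SAP*

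**What the plan says.** The primary safety objective in SAP 2.1 is "To describe the safety profile of all participants in each age group and each study intervention group up to 12 months post-last dose". Protocol Table 3.1 gives the matching endpoint as "Presence of serious adverse events (SAEs) and adverse events of special interest (AESIs) throughout the study", and treats MAAEs the same way.

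For participants who take an authorized COVID-19 vaccine outside the study, the protocol (synopsis, 4.1, the footnote to inclusion criterion I05, and 7.1.2) says that their "data up to the point of receipt of authorized/approved COVID-19 vaccine will be included in the primary analysis for immunogenicity and safety". They then stay in follow-up.

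The SAP carries this out in its main safety analysis. For SAEs (4.4.1.3), "SAEs with time of onset on or after the date of receiving a non-study authorized/approved COVID-19 vaccine will be listed separately". For AESIs (4.4.1.5.7), "AESIs with time of onset on or after the date of receiving a non-study authorized/approved COVID-19 vaccine will be listed separately". For MAAEs (4.4.1.5.8), "MAAEs with time of onset on or after the date of receiving a non-study authorized/approved COVID-19 vaccine will be listed separately". SAP 5.1 repeats the cut for all safety, immunogenicity and efficacy data. SAP 5.7 names among the analyses that will not be done: "Complementary analysis and sensitive analysis on immunogenicity data and safety data".

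On what happened after vaccination and enrollment stopped on 27 September 2021, the SAP (Introduction and 5.7) reports that participants were to be told their intervention so that they could decide about an authorized vaccine. It adds: "Monitoring for SAEs, AESIs, medically attended AEs, and pregnancy and collection of influenza and COVID-19 vaccines were continued with safety calls". The study then ended at the 6-month safety follow-up.

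**The concern.** This is a first-in-human product with a new lipid nanoparticle. Two kinds of AESI can arise late: enhanced COVID-19 on later exposure to the virus, and new-onset chronic conditions. Once participants had been told their arm for the express purpose of choosing an authorized vaccine, taking one became an expected course rather than a rare deviation. The safety calls went on collecting SAEs, AESIs and MAAEs after that point.

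Under the SAP text, whatever those calls found after the outside vaccine appears as listing lines without a count or percentage by group. That includes an SAE that the investigator judged related to the study vaccine. In the summary, such a participant appears as event-free unless an earlier event had already been counted. A reader of a table labelled as covering the whole study would not know that events had been left out.

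**Working it through.** No figure in the plan can be reproduced here: the safety analysis is descriptive and has no power calculation. The check has two parts.

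**1. The provisions side by side**

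| Provision | Period covered |
|---|---|
| Protocol Table 3.1, endpoint | Whole study, no cut at an outside vaccine |
| Protocol 4.1 and 7.1.2, primary analysis | Data up to the outside vaccine; follow-up continues |
| SAP 4.4.1.3, 4.4.1.5.7, 4.4.1.5.8, period definition | All events in the study |
| Same sections, main safety analysis | Onset before the outside vaccine only |
| SAP 5.1 | Data before the outside vaccine; the rest listed |
| SAP 5.1.1.2, SAE, AESI and MAAE summaries | Within 21 days, and the whole study |
| SAP 5.2.2, SafAS | Everyone with at least one injection; no removal at the outside vaccine |
| SAP 5.7 | Complementary and sensitivity safety analyses dropped |

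Calling the censored analysis the main one suggests that a second was once intended, but the SAP text contains none. The whole-study wording in 4.4.1.3 and 5.1.1.2 does not fit the cut in 5.1. Causality does not alter the rule anywhere.

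**2. Possible size**

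The documents give neither uptake nor timing of outside vaccination, so both are assumed. Let u be the share who take an outside vaccine, t the day they take it, and F the length of follow-up, with t and F counted from the same start. F = 180 corresponds to the 6-month point.

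Share of follow-up outside the tables = u × (F − t) / F.

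- Low end: 0.25 × (180 − 90)/180 = 0.125
- High end: 0.75 × (180 − 43)/180 = 0.571

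To turn this into a reported percentage, suppose that 10% of participants would have an event by day 180, with a constant hazard h = −ln(0.90)/180. Participants stay in the SafAS denominator after their events stop counting, so the table shows (1 − u) × 0.10 + u × [1 − exp(−h × t)].

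- Low end: 0.75 × 0.10 + 0.25 × 0.0513 = 0.0878
- High end: 0.25 × 0.10 + 0.75 × 0.0249 = 0.0436

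| Uptake u | Day t | Follow-up outside tables | Shown when the true value is 10% |
|---|---|---|---|
| 25% | 43 | 19.0% | 8.12% |
| 25% | 90 | 12.5% | 8.78% |
| 50% | 43 | 38.1% | 6.24% |
| 50% | 90 | 25.0% | 7.57% |
| 75% | 43 | 57.1% | 4.36% |
| 75% | 90 | 37.5% | 6.35% |

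The third column measures follow-up time, not events. The last column also needs the constant hazard.

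**The case against.** The strongest reply is that the protocol prescribes this cut in several places, so the SAP implements the plan. That stands. The main analysis should stay censored, and nothing here shows an error in it. But the protocol's rule settles which data enter the primary analysis. It does not rule out a supplementary summary, and the same paragraphs keep participants in follow-up.

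A second reply is that events after a different COVID-19 vaccine cannot be cleanly attributed, and that pooling them could inflate counts if the question is the effect of the study vaccine alone. Protocol 9.3 and SAP 5.2.2 also set aside safety data recorded for a vaccine received outside the protocol design. This stands as a reason to keep the two periods apart. It does not justify leaving events judged related to the study vaccine out of every planned count.

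A third reply is that the events are still collected, reported and listed, and that groups are small: at most 44 planned per vaccine group in the Full Enrollment Cohort, with enrollment stopped early. A listing of a few serious events is readable. It still gives no denominator or percentage by group, which a descriptive objective calls for.

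Finally, the table shells are in a separate Tables, Listings and Figures document that was not supplied. A reader might infer that these events enter no table at all. The available text supports only that the SAP itself plans none. Likewise, what the dropped complementary and sensitivity analyses would have contained is not described.

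**Conclusion.** The point holds as a reporting gap and a low-cost improvement. In the SAP text, the by-group SAE, AESI and MAAE summaries describe safety only up to an outside COVID-19 vaccine, and related events get no different treatment. The whole-study labels do not match. With everyone kept in the denominator, the percentages understate the whole-follow-up proportion whenever events occur after the outside vaccine. With 25% to 75% uptake between day 43 and day 90, about 12.5% to 57% of a 180-day follow-up falls outside the tables. Those inputs are assumptions, so the range shows what could happen and is not an estimate.

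Three stronger readings are not supported:

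- A reader might infer that the safety objective goes unanswered. It is answered in the tables up to the outside vaccine, and later events are listed.
- A reader might call the censored counts biased in themselves. That depends on the question: they understate whole-follow-up safety, but are a defensible description of the period before another vaccine.
- A reader might infer that regulators agreed to keep the 6-month follow-up in order to detect late events. The SAP says that the study was shortened from 12 months to 6 after regulatory concurrence, and gives no such purpose. The missed 12-month horizon is a separate matter from this rule.

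**What to change.** - Keep the censored tables as the main safety analysis, and label them as covering onset before any outside COVID-19 vaccine.
- Add to SAP 5.1.1.2, with matching text in 4.4.1.3, 4.4.1.5.7 and 4.4.1.5.8, one supplementary table each for SAEs, AESIs, MAAEs and deaths. Each counts all events from first injection to end of follow-up by intervention received, regardless of outside vaccination. Use separate columns for onset before and on or after the outside vaccine, and a row for events judged related to the study intervention, with missing causality handled as in SAP 5.3.1.2. A participant can appear in both columns, so these need not add up to the total.
- Report by group how many participants took an outside vaccine and the follow-up time before and after it. This replaces the assumed range above with facts.
- Reconcile the whole-study wording in 4.4.1.3 and 5.1.1.2 with the cut in 5.1.

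The cost is a few extra tables from data already collected. The drawback is that later events are partly confounded by the outside vaccine. The split by onset makes this visible but does not remove it.

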4.4.1.4 Laboratory Test Results

Biological safety tests (biochemistry, hematology, urinalysis, and coagulation) will be performed at the local laboratory. Biological endpoints will be assessed on samples taken at screening and D09 for all participants, D30 (only applicable for Sentinel Cohort and Cohort 2), and unscheduled visits based on Investigator's judgment, in cases of abnormal safety laboratory results.

The parameters to be evaluated are detailed in Table 10.1 of the protocol.

Endpoints will be defined as either within or outside normal range. Normal ranges for each endpoint will be provided by the study center. The biological safety information will be entered by the site staff in the appropriate CRF forms along with units and normal ranges. In case of out-of-range values, specific endpoints may be rechecked, and additional biological parameters may be evaluated, based on the Investigator's judgement. This complementary safety information will also be entered by the site staff in the appropriate CRF forms along with units and normal ranges.

Any change in the testing equipment using different ranges should be reported on an ongoing basis to the Sponsor so that any value can be interpreted at a given time against the appropriate range of values.

Biological safety endpoints will be assessed on whether or not they reach the pre-defined intensity levels (Grade 1, 2, or 3) for analytes with applicable toxicity grading, as specified in the protocol. Table 10.4 of the protocol contains the pre-defined intensity scales according to which the biological safety parameters will be assessed. If at least 1 of these intensity levels is reached, the Investigator will evaluate the clinical significance of the results and report clinically significant abnormal values as AEs in the CRF.

If an endpoint reaches the pre-defined intensity threshold but is within the normal range provided by the study center, it will be treated as not reaching the intensity threshold.

4.4.1.5 Other Safety Endpoints

4.4.1.5.1 Pregnancy

This information will be listed as collected. No derivation or imputation will be done.

4.4.1.5.2 Action Taken

Solicited injection site/systemic reactions after any vaccine injection(s) will be summarized by action taken.

4.4.1.5.3 Seriousness

This information will be summarized as collected. No derivation or imputation will be done.

4.4.1.5.4 Outcome

This information will be summarized as collected. No derivation or imputation will be done.

4.4.1.5.5 Causality

This information will be summarized as collected. Missing causality (relationship) will be handled as described in [Section 5.3.1.2](#).

4.4.1.5.6 AEs Leading to Study Discontinuation

A flag will be available in the clinical database for all AEs in order to identify AEs leading to discontinuation.

In general, the items that are counted are:

- For participants disposition: if participants did not complete the study due to AE as recorded in Completion at End of Study form
- For safety overview: if participants did not complete the study due to AE as recorded in Completion at End of Study form or had any solicited or unsolicited AEs causing study discontinuation / termination as recorded in solicited reaction or unsolicited AE forms within the time period indicated

- For summary of unsolicited AEs by system organ class (SOC) / PT: A solicited AE that has “Caused Study Termination” checked that is at least Grade 1 or an unsolicited AE that has “Caused Study Termination” checked that is at least Grade 1 or missing and is within the time period indicated

4.4.1.5.7 AESI

AESIs will be collected throughout the study to ensure that events are communicated to the Sponsor in an expedited manner and followed-up until the end of the follow-up period or resolution, as per the assigned causality.

AESIs will include:

- Protocol-specified AESIs: Anaphylactic reactions, generalized convulsions, Guillain-Barré Syndrome (GBS), acute disseminated encephalomyelitis (ADEM), thrombocytopenia, and vasculitides
- New-onset chronic medical conditions (NOCMCs)
- AESIs related to SARS-CoV-2 infection and COVID-19 disease (see Appendix 10.5 of the protocol).

NOCMCs are defined as any new ICD-10 diagnosis (10th revision of the International Statistical Classification of Diseases and Related Health Problems) that is applied to the participant during the course of the study, after receipt of the study agent, that is expected to continue for at least 3 months and requires continued health care intervention.

AESIs will be analyzed throughout the study using the following periods:

- Within 21 days after each injection
- During the study (ie, all AESIs occurred during entire the study or the cutoff date which corresponds to the date of any interim analysis)

Note: AESI with time of onset before first vaccination (negative time of onset) will not be included in analysis but will be listed separately.

Main safety analysis will include only those AESIs with time of onset before a participant received a non-study authorized/approved COVID-19 vaccine, if applicable. AESIs with time of onset on or after the date of receiving a non-study authorized/approved COVID-19 vaccine will be listed separately.

